3.4 Data handling

All information relative to the study will be recorded into a 21 CFR part 11 FDA compliant electronic Case Report Form (eCRF). Data corrections will be entered by the authorised site personnel.

The Principal Investigator will be responsible for the timeliness, completeness, and accuracy of the information entered on the CRF. The Principal Investigator will

provide access to the Medical Monitor or designated Sponsor representative(s) for the periodic review of all study records, source documents among other records for review and inspection to assure accuracy and completeness of the CRFs. All CRFs will be 100% source verified against corresponding source documentation (e.g. office and clinical laboratory records) for each patient.

4. SUBJECT DISPOSITION AND WITHDRAWAL

4.1 Subject disposition

Subject disposition for each phase and cohort will be presented as both flow chart and table. Each will show: the number of subjects enrolled, and the number of cycles completed in each phase.

4.2 Study completion and withdrawal

A table will present the number and percentage of patients who complete each phase of the study by cohort and where premature withdrawals occur, the reason for each withdrawal.

5. DEMOGRAPHIC AND OTHER CHARACTERISTICS AT BASELINE

5.1 Demographic data

Demographic data collected Screening and the Cycle 1A Day 1 (baseline) visits, including age, gender, height, weight, BMI and race together with other characteristics recorded in the CRF will be summarised by descriptive statistics or frequency tabulations by cohort. If Phase II of the Study is executed, their demographic data will be summarised and presented separately. An 'Overall' column will be presented.

5.2 Disease history

Characteristics of disease history will be summarised and tabulated by cohort and overall within each phase of study. An 'Overall' column will be included in the table.

5.3 Medical history

Medical history events will be coded by using the latest available version of MedDRA. Prior and current events will be summarised and tabulated separately by System Organ Class and Preferred term and cohort. An 'Overall' column will be included in the table.

5.4 Prior medications

Prior medications will those medications taken and ceased prior to the first dose of study drug. Prior medications will be coded by using the latest available version of the WHO DD. Prior medications will be summarised by Levels 1 and 2 codes and terms and by cohort, with an 'Overall' column.

5.5 Concomitant medications

Concomitant medications will be those medications taken during the study treatment period. Concomitant medications will be coded by using the latest available version of the WHO DD. Concomitant medications will be summarised by Levels 1 and 2 codes and terms and by cohort, with an 'Overall' column. New medications will be defined as those drugs commenced after the first dose of the study treatment. New medications will be summarised by Levels 1 and 2 codes and terms and by cohort, with an 'Overall' column.

5.6 Prior treatments

Chemotherapy and other anti-cancer treatments received by patients prior to commencement of this study will be summarised and tabulated by cohort, with an 'Overall' column.

5.7 ECOG status

ECOG status measured at Screening will be summarised and tabulated by cohort, with an 'Overall' column.

6. COMPLIANCE

Compliance will be calculated as the percentage of drug to be given versus what is actually received by each patient within each phase of the study. Compliance will be summarised and tabulated for each cohort with an 'Overall' column.

7. EFFICACY ANALYSES

There are no statistically powered efficacy objectives in this study, however, tumour measurements, RECIST criteria response, progression-free and overall survival will be analysed for signals of treatment efficacy.

7.1 Efficacy

Tumour measurements will be assessed by radiological methods. Longest dimensions for each target lesion within each patient will be summed at each measurement time. Sums will be analysed by descriptive statistics by cohort for each measurement time within each phase of the study.

Response to treatment, as measured by the RECIST criteria, as well as duration of response will be assessed following each radiological assessment. The best overall response and the duration of that response will be summarised and tabulated by cohort. Duration of the objective response will be defined as the time from the initial CR or PR to the time of disease progression or death on study, whichever occurs first.

For patients who are alive and have not experienced disease progression on study, duration of objective response will be censored at the day of the last tumour assessment. Time to disease progression is defined as the time from the first day of study drug administration (Day 1) to disease recurrence or progression on study. Progression free survival (PFS) is defined as the time from the first day of study drug administration (Day 1) to disease recurrence or progression, or death on study. Patients who are alive and disease progression-free will be censored at the date of last disease evaluation. Progression-free survival and overall survival will be analysed using the Kaplan-Meier actuarial method. Median times and 95% confidence intervals will be computed by cohort.

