
Criteria for Evaluation
	
Safety: to be assessed through the analysis of routine laboratory tests (haematology, serum chemistry, urinalysis), physical examinations, vital signs, and ECOG status. Adverse event monitoring will be performed and assessed using the CTCAE National Cancer Institute Common Terminology Criteria for Adverse Events, Version 4.03 (CTCAE) scoring system.
 
Efficacy: All efficacy assessments will be performed at the discretion of the Investigator but at a minimum should include a baseline assessment (CT scan, ECOG assessment) and follow-up assessments at a minimum of every 12 weeks while receiving study drug. Tumor response and progression-free survival will be assessed using standard RECIST criteria.
 
Pharmacokinetics: blood and 24 hour-urine samples will be analysed to determine the primary idronoxil metabolites and the primary route of excretion.
 
Biomarkers: Ceramide and sphingosine-1-phosphate (related to the molecular target of idronoxil) and ENOX2 will be assessed at baseline and at completion of idronoxil therapy per cycle. Biomarker and plasma idronoxil levels to be correlated with anti-cancer activity and any toxicity.

Statistical Methods
	
Statistical analyses will be primarily descriptive in nature and statistical hypothesis testing will not be performed. All patients will be included in the evaluation of safety. Data will be presented by Cohort, by idronoxil and carboplatin dosages, and by tumour type.

Inclusion Criteria
	
 
1. Provision of informed consent.
 
2. Male or female <math>\geq 18</math> years of age.
 

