## 9.3 DURATION OF STUDY TREATMENT

Patients can continue to receive combination therapy of idronoxil and carboplatin at their allocated dose level for:

- up to 6 (six) 28-day treatment cycles OR
- until demonstrated radiologic and/or clinically assessed progressive disease OR
- until another withdrawal criterion is met (See Section 7.4).

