### **13.3 PROCEDURES FOR HANDLING MISSING, UNUSED AND SPURIOUS DATA**

No imputation of values for missing data will be performed. Standard clinical monitoring and data management practices will be used to ensure the integrity of the data.

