2.2 Study design

This is a Phase I, open-label, non-randomised, dose-escalation (two-step) study of the experimental drug, NOX66, in a suppository dosage formulation (NOX66) in patients with refractory solid tumours that have stopped responding to standard treatment options. The patients will have solid cancers selected from 5 phenotypes: prostate, breast, ovarian, lung, head and neck.

The study has two confirmed arms: a Phase Ia (Run-In) Arm where NOX66 is used alone and a Phase Ib (Combination) Arm where NOX66 is used in combination with carboplatin.

A Phase IIa arm is a potential third arm. This will only be triggered by clinical responses in the Phase Ib arm that are considered by the Investigators to be meaningful.

Sixteen (16) evaluable patients will be recruited and 8 patients allocated to each of two cohorts – Cohort 1 and Cohort 2. Cohort 1 will receive an NOX66 dosage of 400 mg daily; Cohort 2, 800 mg daily. Recruitment into Cohort 2 will not occur until at least 7/8 Cohort 1 patients have completed at least 1 Phase Ia Treatment Cycle without Dose-limiting Toxicity (DLT).

In the **Phase Ia (Run-In) Arm**, patients will self-administer NOX66 rectally either once or twice (12-hourly) daily for 14 consecutive days for one (21-day) Treatment Cycle.

The main purpose of the Phase Ia Arm is to confirm the tolerability of NOX66 formulation when used for 14 consecutive days in a 21-day monotherapy cycle..

The **Phase Ib (Combination) Arm** will commence immediately following the Phase Ia (Run-In) Arm and will comprise NOX66 being administered in combination with carboplatin. Patients will continue in the same cohorts and remain on the same NOX66 dosage.

Within each 28-day combination treatment cycle, NOX66 treatment will commence on Day 1 and continue daily for 7 consecutive days; carboplatin will be administered intravenously on Day 2.

There will be two different dosages of carboplatin administered: AUC = 4 (600 mg maximum) and AUC = 6 (900 mg maximum). Patients will start with the lower dose and receive that for 3 Treatment Cycles, then progress onto the higher dosage of carboplatin which they will receive for up to a further 3 Treatment Cycles.

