3.3 General statistical methodology

Patients will be analysed by both study arm and dose cohort. Patients will be assigned sequentially to the two cohorts of 400 mg NOX66 (1 suppository per day) or 800 mg NOX66 (2 suppositories per day). Each cohort will be identified by '400 mg' or '800 mg'. The first 16 patients recruited to the study will be included in the study arm identified as 'Phase I' that will consist of a 21-day monotherapy phase and combination phase of up to 6 x 28-day cycles. Additional replaced patients will be included in the combination phase of up to 6 x 28-day cycles with the highest tolerated NOX66 dose cohort.

Descriptive statistics or continuous measures will include number of observations (n), mean, standard deviations (SD), minimum, median and maximum. For categorical measures, the descriptive statistics will include count and percent of the cohort.

There are four investigative sites in this study. There will be no analysis by study site.

The Medical Dictionary for Regulatory Affairs (MedDRA) will be used to code both medical history events and adverse events recorded during the study. The latest available version of MedDRA will be used to perform the coding at the end of the study. The World Health Organization (WHO) Drug Dictionary (DD) will be used to code concomitant medications taken prior to and during the study treatment period. The latest available version of WHO DD will be used to perform the coding at the end of the study.

As this is a dose escalation study, an 'Overall' column will be calculated for all tables.

All programming will be done in SAS version 9.4.

Missing data will remain missing with the exception that, for safety data, if there are corresponding unscheduled visits where data values exist, and those data are missing for the prior, scheduled, visit, then the values from the unscheduled visit will be imputed.

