11. TABLE AND FIGURE LISTINGS

Table Section	Table Title (Population)
Section 10.1	Patient disposition (All populations)
	Completion and withdrawal (Safety population)
Section 11.2	Demographics (Safety population)
	Disease history (Safety population)
	Prior medical history events (Safety population)
	Current medical history events (Safety population)
	Prior medications (Safety population)
	Concomitant medications (Safety population)
	New medications (Safety population)
	Prior chemotherapy (Safety population)
	ECOG status (Safety population)
Section 11.3	Compliance (Safety population)
Section 11.4	Tumour measurements (Efficacy population)
	RECIST response rates and durations (Efficacy population)
	Progression-free survival (Efficacy population)
	Overall survival (Efficacy population)
	Plasma concentrations (PK population)
	Pharmacokinetic coefficients (PK population)
Section 12.1	Exposure (Safety population)
Section 12.2	Summary of adverse events (Safety population)
	Pre-treatment adverse events (Safety population)
	Treatment emergent adverse events (Safety population)
	Treatment emergent adverse events considered possibly, probably or definitely related to study treatment (Safety population)
	Severe adverse events (Safety population)
	Adverse events resulting in withdrawal (Safety population)
Section 12.3	Deaths and serious adverse events
Section 12.4	Serum biochemistry (Safety population)
	Biochemistry shift table (Safety population)
	Haematology (Safety population)
	Haematology shift table (Safety population)
	Categorical urinalysis results (Safety population)

Section 12.5	Urinary pH and specific gravity (Safety population)
	Urinary microscopy (Safety population)
	Vital signs (Safety population)
	Physical examination (Safety population)
	ECG parameters (Safety population)
	ECG findings (Safety population)
	Biomarkers (Safety population)

Figure Section	Figure Title (Population)
Section 11.4	Tumour measurements (Efficacy population)
	Pattern of response by cohort (Efficacy population)
	Progression-free survival (Efficacy population)
	Overall survival (Efficacy population)
	Plasma concentrations by cohort (PK population)
Section 12.2	Most common preferred terms (Safety population)
Section 12.5	Biomarkers (for each parameter) (Safety population)

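### Tumour burden is described only as raw lesion sums by cohort at each scan, so summaries after the first follow-up scan compare different patients and can mislead in either direction

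*SAP*

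**What the plan says.** SAP 7.1 sums the longest target-lesion dimensions within each patient and then says: "Sums will be analysed by descriptive statistics by cohort for each measurement time within each phase of the study". SAP 3.3 defines the statistics: "Descriptive statistics or continuous measures will include number of observations (n), mean, standard deviations (SD), minimum, median and maximum". SAP 11 lists a table and a figure under the title "Tumour measurements (Efficacy population"; the form of the figure is not stated. SAP 7 names tumour measurements among the results to be searched for signs of activity.

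Four provisions decide who contributes at later scans:

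- Protocol 9.3 lets combination therapy run for up to six 28-day cycles or "until demonstrated radiologic and/or clinically assessed progressive disease OR" another withdrawal criterion applies.
- The synopsis (Criteria for Evaluation) requires "follow-up assessments at a minimum of every 12 weeks while receiving study drug". Protocol 10.3.1 leaves timing within that limit to the investigator.
- SAP 3.3: "Missing data will remain missing with the exception that, for safety data", values from unscheduled visits may be used. Tumour sums have no such exception.
- Protocol 13.3: "No imputation of values for missing data will be performed".

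For vital signs (SAP 8.4), laboratory values (8.5) and biomarkers (8.6) the SAP does plan change from baseline.

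**The concern.** A raw sum mixes two things: how large a patient's disease was at entry and how it has changed. Across successive scans the mean or median can be read as a trend only if the same patients are measured each time. Here they are not. Patients who progress come off treatment, need not be scanned again and have nothing carried forward. The summary at a later scan therefore describes a smaller group, selected for not having progressed, and is set beside a baseline figure for everyone.

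The stake is a misread activity display. With eight patients per cohort, one or two departures are enough to move the mean by more than a modest treatment effect would. A reader could take a falling line for shrinkage, or miss growth that ended treatment in the patients no longer counted.

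**Working it through.** The documents give no expected lesion sizes, growth rates or attrition, so there is no planned figure to reproduce. Every size below is an assumption that shows the mechanism; none is a prediction.

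**Inputs from the documents.** Cohort size is 8 (SAP 2.2: "Sixteen (16) evaluable patients will be recruited and 8 patients allocated to each of two cohorts"). The maximum scan interval is 12 weeks. Planned combination treatment is 6 × 28 = 168 days = 24 weeks. The minimum schedule therefore gives about 24 / 12 = 2 post-baseline scans on treatment.

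**1. Worked cohort of 8 (assumed baseline sums 40, 50, 60, 70, 80, 90, 120, 140 mm).** The two largest grow 25% by the first follow-up scan, are recorded as progressed and are not scanned again. The other six do not change.

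- Baseline: mean 650 / 8 = 81.25 mm; median (70 + 80) / 2 = 75 mm.
- First follow-up: 120 × 1.25 = 150 and 140 × 1.25 = 175. Mean (390 + 150 + 175) / 8 = 89.4 mm; median 75 mm.
- Second follow-up, six patients: mean 390 / 6 = 65.0 mm; median (60 + 70) / 2 = 65 mm.
- Apparent change in the mean: 65 / 81.25 − 1 = −20% from baseline, and 65 / 89.375 − 1 = −27% from the first follow-up.

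No tumour shrank. The six patients still scanned have a paired change of 0%.

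**2. Direction.** Let any two of the eight leave, with the others unchanged. There are 28 possible pairs. The mean falls when the pair's baseline sums total more than 2 × 81.25 = 162.5 mm, which holds for 13 pairs (13 / 28 = 46%). The extremes are −20% (the two largest leave) and 560 / 6 = 93.3 mm, or +15% (the two smallest leave).

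**3. Simulation of 20,000 cohorts of 8.** Assumptions: log-normal baseline sums with mean 80 mm and the coefficient of variation (CV) shown; log growth averaging 0.10 per interval, with SD 0.20 in the first interval and none in the second; patients at least 20% above baseline at the first follow-up leave (about one third); correlation between baseline size and growth as shown. The full-cohort and raw-mean columns compare the second follow-up with the baseline mean of all eight.

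| CV | Correlation | True change, all patients | Raw mean, remaining | Mean paired change, remaining | Cohorts where raw mean fell but true mean rose |
|---|---|---|---|---|---|
| 0.4 | 0 | +24.4% | +10.2% | +10.3% | 20% |
| 0.4 | 0.3 | +27.1% | +4.3% | +10.4% | 35% |
| 0.4 | 0.6 | +29.6% | −2.1% | +10.3% | 52% |
| 0.6 | 0 | +24.7% | +10.2% | +10.3% | 26% |
| 0.6 | 0.3 | +28.2% | +1.5% | +10.3% | 43% |
| 0.6 | 0.6 | +31.8% | −7.7% | +10.2% | 62% |
| 0.8 | 0 | +24.8% | +10.4% | +10.3% | 29% |
| 0.8 | 0.3 | +29.1% | −0.6% | +10.3% | 47% |
| 0.8 | 0.6 | +33.6% | −12.2% | +10.2% | 66% |

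In every row the raw mean understates growth. An average fall below baseline appears only when larger tumours also grow faster.

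**4. What a per-patient summary shows.** In the worked cohort, best percent change for all eight gives six patients at 0% and two at +25%, mean (2 × 25) / 8 = +6.25%. In the simulation, paired change among those remaining is about +10% against a true +24% to +34%. Pairing removes the change in composition; keeping the leavers is also needed to deal with the selection.

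**The case against.** The strongest reply is that this table carries little weight. RECIST response and progression are judged within each patient. Patients who progress count in best overall response and as PFS events, and Protocol 13.2 treats patients with too little data as non-responders. Phase IIa depends on RECIST responses, no hypothesis is tested, and no decision uses the mean sum. All of that stands and limits the severity. A reader might infer from SAP 7.1 that within-patient change is ignored altogether; the documents do not support that. What is absent is a continuous change measure for the sums.

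Second, n is already among the planned statistics and all data are listed, so attrition would be visible. That stands, but a falling n discloses the problem without correcting it, and the median moves too. The figure might turn out to show individual lines; the SAP does not commit to that.

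Third, the scan that documents progression is itself a measurement, so the first follow-up summary still includes those patients. This is right: the effect starts after that scan. Some patients may also be scanned after progression, but nothing requires it.

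Two other strong readings go too far. One is that the mean will fall: the direction depends on who leaves, and with growth unrelated to size the average result is hidden growth, not apparent shrinkage. The other is that a fall would coincide with the step from AUC 4 to AUC 6 and pass for a dose response. Three 28-day cycles do equal the 12-week maximum interval, but scan timing is discretionary, so the documents do not establish that the two coincide.

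**Conclusion.** The point holds for one descriptive efficacy table and its figure. After the first follow-up scan, the planned summaries of raw sums compare different sets of patients and can hide growth, or show a fall or a rise, through who remains alone. In the assumed cohort the artefact is −20% from baseline; across all pairs of leavers it runs from −20% to +15%. The sizes rest entirely on assumed lesion sums, growth and departures. The mechanism rests on the documents: treatment and required scanning end at progression, efficacy data are not imputed, and no change from baseline is planned for the sums. RECIST best response, PFS and OS are unaffected. Severity is minor to moderate.

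**What to change.** In SAP 7.1, and for the Tumour measurements table and figure in SAP 11:

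1. Report each patient's percent change from baseline at every scan, shown as an individual profile plot by cohort.
2. Report each patient's best percent change as a waterfall plot by cohort, for the whole efficacy population including those who leave for progression.
3. If per-visit summaries of sums are kept, label them as covering only patients still scanned, and give n and the reasons for missing scans at each time.
4. List separately any treated patients who had no follow-up scan because of progression or death. SAP 3.1 places them outside the efficacy population, so they would otherwise not appear in these displays; a listing avoids redefining that population.

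The cost is SAP wording, modest programming and one extra listing. No new assessments or measurements are needed, because the baseline and follow-up sums are already collected.
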